8.7.3 Clinical Trial

Raseline

Data gathered for the registry may be used as the baseline data for the randomised trial providing the dates are the same. If the dates differ, tests as shown in the schedule of assessments should be repeated. In addition, the following tests and measurements are mandatory prior to randomisation:

- 1. Blood collection for biomarkers
- 2. EQ5D and KCCQ questionnaires
- 3. Walk Tests
- **4.** Electronic transmission of the ECG: record and transmit 12-lead ECG to the Glasgow electrocardiology core laboratory. ECGs will be identified only by participant registration number.

Follow-up

Assessments will be repeated as at baseline on Days 7 and 60 and at 6, 12 and 24 months.

For safety visits (in addition to those above), vital signs consist only of measurements of heart rate, blood pressure and oedema grade and for biochemistry only includes sodium, potassium, urea and creatinine.

A Patient Global Assessment (PGA) which assesses the change compared to baseline will also be done at each follow-up visit as an assessment of symptoms.

Trial assessments

There will be two types of clinical assessments in this trial

a) Assessments for Efficacy at 7 and 60 days and at 6, 12 and 24 months

b) Assessments for Safety at 1, 3, 5, 14, 30days and at 3, 9, 15, 18, 21, 27 months and every 3 months thereafter until the end of the trial.

Visits for assessment of efficacy require all baseline assessments to be repeated with the exception of demography and prior medical history. Echocardiography is optional.

Visits for assessment of safety require evaluation only of symptoms, weight, concomitant cardiovascular therapy, severity of oedema, blood pressure and a blood test for measurement of serum sodium, potassium, urea and creatinine.

Longer-term efficacy and safety during the randomised trial will be assessed by reports of adverse reactions, serious adverse events and the primary composite endpoint and its components.

Participants should be encouraged at each visit to bring any remaining trial medicines (patiromer/spironolactone or eplerenone). An assessment of compliance will be made at each trial visit by research staff and documented in the eCRF. Unused IMP should be returned to the site pharmacy where it will be logged and disposed of safely.

Participant retention in the randomised trial will be enhanced by regular contact with the research team and a "frequently asked questions & answers" section on a publicly accessible trial website.

Investigators will be asked to interrogate their own hospital's electronic record to identify hospitalisations and deaths for randomised patient on a quarterly basis to ensure that events that the participant fails to mention are recorded.

Most patients will initially be hospitalised. NICE guidance recommend that patients with heart failure should be evaluated by an expert at least once every 6 months but patients with advanced heart failure require more intensive surveillance and management. Accordingly, many (more than half) of these evaluations would be required for routine care.

Vaccine Follow-Up

The following details will be captured at 6, 12 and 24 months:

- COVID vaccination details
- Other vaccination details (including but not limited to influenza, pneumococcal, and shingles vaccination)

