Trial Participants	and serum potassium >5.0mmol/L	People with heart failure, worsening symptoms and signs of congestion and serum potassium >5.0mmol/L (participants may or may not already pe receiving a mineralocorticoid antagonist)					
Planned Sample Size	Phase A: 400 participants completing	ng 60 days follow-up					
	Phase B: 2,000 participants						
Treatment duration	Up to 5 years						
Follow up duration	Trial follow-up will continue until a raprimary outcome event. It is antic approximately 5 years after recruitments						
	Patients will be followed by linkage hospitalisation and death for up to 8	to their electronic medical records for years after trial completion.					
Planned Trial Period	Up to 5 years						
	Objectives	Outcome Measures					
Primary for the Randomised Trial (long- term follow-up)	To reduce morbidity and mortality	Composite of time to need for parenteral diuretic therapy (subsequent to initial discharge) for worsening or recalcitrant heart failure, (re-)hospitalisation for worsening heart failure or non-cancer deaths.					
Other Primary	Registry:	Registry:					
	To assess morbidity and mortality	Composite of time to (re-)hospitalisation or death					
	Randomised Trial -to Day 60:	Randomised Trial -to Day 60:					
	To improve congestion	"Congestion Index" on Day 60					
Key Secondary	Registry: • To describe participants characteristics and assess morbidity and mortality (Note that the registry also includes all patients in the randomised trial.)	Registry Time to cardiovascular (re-)hospitalisation or non-cancer death Time to heart failure (re-)hospitalisation or non-cancer death					

Version 5.0 22 July 2021 Page 9 of 82

		 Incidence rate for hospitalisation (all-causes, cardiovascular causes, heart failure causes, cancer causes – separately) Time to death (all-causes, cardiovascular causes, heart failure causes, cancer causes,
		and other)
Key Secondary	Randomised Trial – to Day 60:	Randomised Trial – to Day 60:
	Dose of MRA achieved	Dose of MRA (Days 7 & 60)
	Further evidence of improved apparentian	Congestion Index (Days 7& 60)
	congestion	Days dead or hospitalised during the first 60 days
		 Individual Components of the Congestion Index (Days 7 &60)
		Quality of Life at (Days 7 &60)
		NYHA class (Days 7 &60)
		Patient Global Assessment (PGA) (Days 7 &60)
Key Secondary	Randomised Trial (long-term follow-up):	Randomised Trial (long-term follow-up):
	To reduce mortality	Mortality
	To reduce morbidity, increase	- All-Cause

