4.7 Secondary Endpoints

Registry

- Time to first cardiovascular (re-)hospitalisation or non-cancer death as judged by primary and secondary ICD-10 codes
- Time to first heart failure (re-)hospitalisation or non-cancer death as judged by primary and secondary ICD-10 codes
- Incidence-rate for hospitalisation, all-causes and due separately to cardiovascular causes, heart failure or cancer, and other as judged by primary and secondary ICD-10 codes
- Time to death
 - All-cause and due to cardiovascular, heart failure, cancer and other based on hospitalisation data and death certificates.

The data for all registry outcome events will be obtained solely by linkage to electronic medical records.

Randomised Trial until Day 60

- Dose of MRA (Days 7 & 60)
- Congestion Index (Days 7& 60)
- Days dead or hospitalised during the first 60 days
- Individual Components of the Congestion Index (Days 7 &60)
- Quality of Life at (Days 7 &60)
- NYHA class (Days 7 &60)
- Patient Global Assessment (PGA) (Days 7 &60)

Randomised Trial (long-term follow-up)

- Mortality
 - All-Cause
 - Non-Cancer

- Cardiovascular
- Days lost to hospitalisation for heart failure or non-cancer mortality over 12 months
- Days lost to any hospitalisation or death over 12 months
- Quality adjusted life-years for the duration of the trial using EQ5D
- Proportion alive & well at 12 months (well-being defined by KCCQ quality of life score)
- Dose of MRA taken at the time of the 6 and 12 month visits
- Dose of oral diuretics other than MRA taken at the time of the 6 and 12 month visits
- NYHA class at 6 and 12 months
- Patient Global Assessment (PGA) at 6 and 12 months

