6. TRIAL SETTING

This is a multi-centre trial that will be conducted in approximately 100 UK NHS Trusts/Boards responsible for managing patients with heart failure who have sufficiently severe manifestations of congestion that they are being considered for intravenous diuretic therapy.

Principal investigators will be experts in the management of heart failure and may either be a) doctors or b) nurses/pharmacists working under the supervision of a doctor with expertise in the management of heart failure. The TSC will review the curricula vitae of all proposed principal investigators to ensure they are suitably qualified and experienced to conduct the trial with adequate support. Either a principal investigator who is medically qualified or a designated medical practitioner on the delegation log will verify that all inclusion/exclusion criteria have been met. Doctors and appropriately qualified non-medical prescribers who have been delegated this task by the local principal investigator may prescribe MRA and patiromer as described in this protocol and as randomly assigned, provided this is in accordance with local policies and procedures.

Participants are typically 'known' to heart failure services and are hospitalised or require intensive management either as day-cases or by community heart failure services.

Participants will be identified from primary or secondary care services, including hospital wards and clinics and community heart failure services. The precise set-up of heart failure services/pathways will vary according to locality. If a patient moves away from their original trial site and they can attend visits at an alternative trial site they may continue with their randomised treatment allocation. Otherwise, patients will be withdrawn from trial follow-up visits and those assigned to receive patiromer will revert to standard care. These patients will continue to be followed for hospitalisations and deaths by the investigators until the end of the trial or by record linkage in the extended follow-up phase.

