8.1.2 Schedule of Procedures for the Randomised Trial (long-term follow-up)

		Majority of care at follow-up in clinic									
Visit	T7	T8	T9	T10	T11	T12	T13	T14	TX	EOS	
Months	3	6	9	12	15	18	21	24	+3		
Window +/- days	14	14	14	14	14	14	14	14	14	NA	
Consent											
History											
Symptoms/NYHA	Х	Х	Х	Х	Х	Х	Х	Х	Х	Х	
PGA	Х	Х	Х	Х	Х	Х	Х	Х	Х	Х	
CV Therapy	Х	Х	Х	Х	Х	Х	Х	Х	Х	Х	
Non-CV Med		Х		Х				Х			
Height											
Weight	Х	Х	Х	Х	Х	Х	Х	Х	Х	Х	
Vital Signs	Х	X*	Х	Χ*	Х	Х	Х	Χ*	Х	Х	
Physical Exam											
Oedema Grade	Χ	X	X	X	X	X	X	X	Х	X	
Orthopnoea Test		X		X				X			
ECG trace											
Electronic ECG		X		X				X			
Echocardiogram		Opt		Opt				Opt			
Haematology		X		X				X			
Biochem Safety	Χ		X		Χ	X	Χ		X	X	
Biochem+		Х		X				X			
Spot Urine		X		Х				Х			
Biomarkers		Х		Х				Х			
KCCQ/EQ5D		Х		Х				Х			
Walk Test @		Х		Х				Х			
Titration/Compliance	Χ	Х	X	X	Χ	Χ	Χ	X	X	X	
AE/ SAE	Х	Х	Х	Х	Х	Х	Х	Х	X	X	
Dispensing	Χ	X	X	X	Χ	Х	Χ	X	Х		

T = titration visit. TX = repeat visits every 3 months for dispensing and titration. EOS = end of trial. CV = cardiovascular. X* vital signs measured during orthopnoea (orthop) test. Opt = optional

KCCQ = Kansas City Cardiomyopathy Questionnaire. EQ5D = EuroQol 5-dimension questionnaire. NYHA = New York Heart Association functional class. PGA = patient global assessment on a 7-point scale ranging from much worse to much better.

@ for patients who feel unable to do these tests, the reason will be recorded. AE / SAE = adverse / serious adverse events.

Key visits for the assessment of clinical efficacy and endpoints are

- Day 7 (+/-3 days or discharge from hospital or day-care)
- Day 60 (+/-14 days)
- And at 6 months (+/-14 days) months,12 months (+/- one month) and 24 months (+/- one month)

Additional visits are required to assess symptoms and safety (serum potassium/magnesium, renal function, blood pressure). Patients may be evaluated in the community or clinic setting as convenient but will have to attend hospital visits to obtain trial IMP (patiromer, spironolactone/eplerenone).

In addition, if doses of patiromer or MRA are changed, blood pressure and serum electrolytes and creatinine should be re-checked both after 7-12 days and after 30-45 days. If the patient becomes acutely unwell for any reason, blood pressure, serum electrolytes and creatinine should be re-checked. Serum potassium should also be checked within 48 hours of stopping patiromer.

Version 5.0 22 July 2021 Page 30 of 82

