8.3 Consent

In accordance with Health Research Authority guidance, a de-identified register of all potential participants will be kept (Section 7.1 of CTIMP Protocol Development Tool: ".give details including information to be collected regarding participants who are screened but not randomised or reporting the generalisability of the results including the reason not eligible for trial participation, or if they are eligible but declined").

Informed consent for the registry and trial will be obtained by medical staff or delegated support staff with appropriate training. A medical practitioner, either the principal investigator or delegated medical co-investigator, will verify that all inclusion/exclusion criteria have been met.

Potential registry participants with worsening heart failure, who fulfil the inclusion criteria, will be invited to read an ethics committee-approved participant information sheet and provide written consent (Consent Form 1) for inclusion in the registry. We will ask patients who participate in the registry whether they are happy to be contacted about future (hypothetical) research, either observational or randomised trials. This may include sending questionnaires directly to participants. However, enrolment in further trials would only be done in collaboration with local investigators and care-teams. Consent will specifically be sought for the collection and use of routine clinical data for research purposes and for long-term follow-up through the participant's electronic medical record (e.g. Hospital Episode Statistics).

Potential trial participants will be identified from amongst those consenting to the registry. Registry participants who fulfil the trial's inclusion/exclusion criteria will be invited to read an ethics committee-

Version 5.0 22 July 2021 Page 31 of 82

approved participant information sheet and provide written consent (Consent Form 2) for the trial before any research-related procedures are done.

Following written consent, each signature will be dated by the signatory, the original retained in the site file, one copy provided to the patient/relative, one copy inserted into the patient's medical notes and a scanned electronic copy uploaded via the trial web portal and stored at the University of Glasgow (Glasgow Clinical Trials Unit).

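### The back-up search for trial events covers only the site's own hospital, and the plan does not say that its record linkage feeds the primary endpoint

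*Protocol*

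**What the plan says.** **Events in randomised patients.** AEs and SAEs are reviewed at every scheduled visit (Protocol 8.1.1 and 8.1.2). Behind that, Section 8.7.3 sets a second line: "Investigators will be asked to interrogate their own hospital's electronic record to identify hospitalisations and deaths for randomised patient on a quarterly basis". Its stated purpose is "to ensure that events that the participant fails to mention are recorded".

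**Linkage.** Section 8.3 seeks consent from registry participants for long-term follow-up through electronic records, with Hospital Episode Statistics as the example. Trial participants are drawn from those who gave that consent. For the registry, Section 4.7 states: "The data for all registry outcome events will be obtained solely by linkage to electronic medical records". Section 4.9 has registry outcomes evaluated periodically. The Trial Summary adds: "Note that the registry also includes all patients in the randomised trial".

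**Patients who move away.** Under Section 6, a patient who moves may transfer to another trial site. One who cannot is withdrawn from trial visits but is still "followed for hospitalisations and deaths by the investigators until the end of the trial or by record linkage in the extended follow-up phase". Section 8.8 also places linkage after the end of the trial.

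**Other mentions of record follow-up.** Section 8.3 (participants who lose capacity), Section 8.9 (levels of withdrawal) and Section 9.13 (participants who decline visits) each refer to follow-up through medical or electronic records. Section 8.8 uses the electronic record in dating loss to follow-up.

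**The concern.** The back-up exists to find events that the patient does not report, but it looks only where the investigator works. An unmentioned admission to another trust is exactly such an event, and an own-hospital search cannot be relied on to show it. The same holds for a death elsewhere. The weak spot is the patient who has moved or stopped attending: visit reporting has ended, and the own-hospital record is least likely to hold the event.

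The sponsor could therefore hold linked admissions and deaths for randomised patients, gathered for the registry, that never reach the trial endpoint. Blinded adjudication (Sections 5 and 8.5) does not help, because it protects how events are classified and not whether they are found. Section 11.7 says that imputation is not necessary for morbidity and mortality data, which presumes near-complete capture. The primary analysis counts recurrent events (Section 11.3), so a missed later admission is lost information too.

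**Working it through.** **Step 1: the plan's own figure.** Inputs from Protocol 11.1 and SAP 1.5 are a 40% control event rate, 999 per group, 719 first events, and the targets HR 0.75 at 1% and HR 0.80 at 5%. Allocation is 1:1. Two-sided tests are assumed, since sidedness is not stated.

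- Events needed = 4(z for alpha/2 + z for power)² / (ln HR)². For HR 0.75, alpha 1% and 90% power this is 4(2.576 + 1.282)² / (0.2877)², or 720 after rounding up. The plan states 719.
- Power = Phi(|ln HR| × √(events/4) − z for alpha/2). At 719 events it is 90.0% (HR 0.75, 1%) and 84.9% (HR 0.80, 5%).
- Expected events under proportional hazards at HR 0.75: 999 × (0.40 + 1 − 0.60^0.75) = 999 × 0.7183 = 717.6.

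The sample size reproduces within rounding and is not in question.

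**Step 2: share of events missed.** The documents give no share of admissions or deaths outside the site hospital, so a range has to be assumed. An event is exposed only if it is both elsewhere and unreported.

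- Low end: 5% elsewhere, one in five of those unreported: 0.05 × 0.20 = 1%.
- High end: 20% elsewhere, half of those unreported: 0.20 × 0.50 = 10%.

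**Step 3: equal misses in both arms.** The trial ends at 750 observed first events (Section 8.11), so the main effect is delay. True first events needed = 750 / (1 − m):

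| Missed (m) | True first events needed |
|---|---|
| 1% | 750 / 0.99 = 758 |
| 5% | 750 / 0.95 = 789 |
| 10% | 750 / 0.90 = 833 |

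This treats a patient whose first event is missed as never counted. If a later event is captured, the patient enters the count then, and the delay is smaller.

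If calendar time were fixed instead, starting from 719 events, 5% missed would leave 683 events (power 88.2% at HR 0.75 and about 83% at HR 0.80). With 10% missed, 647 would remain (86.1% and 81.0%).

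**Step 4: unequal misses.** As an approximation, observed HR = true HR × (1 − missed, patiromer) / (1 − missed, control). Both directions are illustrations only:

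| Missed, patiromer / control | True HR 1.00 reads | True HR 0.80 reads |
|---|---|---|
| 10% / 5% | 0.90/0.95 = 0.95 | 0.80 × 0.90/0.95 = 0.76 |
| 5% / 10% | 0.95/0.90 = 1.06 | 0.80 × 0.95/0.90 = 0.84 |

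Nothing in the documents selects a row or shows that the arms would differ at all.

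**The case against.** **Other capture routes.** The own-hospital search is only the second line. SAE review takes place at visits no more than three months apart after Day 60. Assessments continue off treatment as far as possible (8.9), and all patients are to be contacted at the end of the trial (8.11). Deaths are reported as SAEs (10.5). Patients carry a safety card, and primary care physicians are written to (Section 3). This stands. It limits the exposure to events missed by every route, but none of these routes is a systematic search beyond the site's hospital.

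**Linkage excluded from the trial.** A reader might infer that the plan bars linked data from the primary endpoint. The documents do not support that. Sections 8.3, 8.9 and 9.13 describe record follow-up of some randomised participants, and Section 10.4 has the committee review all potential endpoints without restricting their source. The plan is silent on whether linked events count, and that silence is the point.

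**Unequal contact by arm.** A reader might infer that patiromer patients are seen more often because patients "will have to attend hospital visits to obtain trial IMP". The same sentence covers spironolactone and eplerenone, so controls on an MRA also collect trial supplies, and both arms share one visit schedule. Up to 25% of controls are expected to tolerate no MRA (Section 2), but they keep their scheduled visits. A bias against patiromer, or a power loss computed from one, is therefore not established.

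**Limits of linkage.** Linkage may not identify parenteral diuretics given without admission, which are part of the primary endpoint (4.5). This also stands.

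**Conclusion.** The point holds as a gap in the stated method of finding events. The only systematic back-up is confined to the site's own hospital, and a wider source that is already planned and consented to is not stated to feed the endpoint or the committee. The events at risk are admissions and deaths that are both elsewhere and unreported, chiefly in patients who move away or stop attending.

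The size is unknown. On an assumed 1-10% missed equally, about 8 to 83 true first events beyond 750 would be needed (758 − 750 and 833 − 750). Any unequal capture would bias the hazard ratio, in a direction that cannot be read from the documents. The sample-size calculation is not in error. The trial closed with four patients randomised and no formal analysis planned (SAP 1.6.1 and 1.6.3), so no reported result is affected. The change is worth making in a design of this kind because it is cheap.

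**What to change.** In Section 8.7.3, state that before the end-of-trial database lock all randomised participants, except those who withdrew from record follow-up, are linked to national hospital and death records up to the end-of-trial date. Any admission or death not already reported goes to the site for source documents and then to the blinded endpoints committee. Keep the quarterly own-hospital search as the interim check. Make Section 6 and Section 8.8 consistent with this, so that linkage is not described only as a post-trial activity.

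The cost is protocol wording and one linkage extract timed before lock, using consent and identifiers already planned for the registry. There are three downsides. Linkage lag and approvals may delay lock. Sites must request some records from other hospitals. Parenteral diuretics given without admission would still depend on site and participant reporting.

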8.8 Long term follow-up after trial completion

At the end of the trial, participants will be returned to usual care as defined by local and national guidelines at that time. The results of the trial may of course have an impact on these guidelines and the future care of patients with heart failure.

Patients will be followed through their electronic medical records via record linkage for up to 10 years after the end of the trial. This will not interfere with their routine care.

Patients will be deemed lost to follow-up on the date that contact with the investigator team ceases or the date on which the last event is recorded in their electronic medical record, whichever is later.

8.9 Withdrawal criteria

Participants may choose to withdraw at any time, either from the intervention (patiromer or MRA), the follow-up procedures or from follow-up through their electronic medical record. Reasons for withdrawal will be recorded, providing the participant agrees. Participants who withdraw from the intervention or

Version 5.0 22 July 2021 Page 42 of 82

follow-up procedures should cease to take IMP and revert to standard-care. The costs of patiromer or MRA would no longer be reimbursed from the trial budget.

Participants who choose to stop patiromer-IMP only should have the dose of MRA adjusted to prevent hyperkalaemia. Participants who choose to stop MRA-IMP only should have the dose of patiromer adjusted to prevent hypokalaemia. Further guidance is provided in Appendix 3. Changes in serum potassium and clinical status should be evaluated carefully after any dose adjustments.

Participants may be withdrawn from IMP by their investigators if deemed appropriate (e.g. the investigator is concerned about a participant's safety because of uncertainty about adherence to IMP). Safety will be assessed by research nurses and/or investigators at each visit and after the occurrence of each SAE/SAR. Participants who have had an SAR (e.g. a hospital admission for the management of hyper- or hypo-kalaemia) should be reassessed for their ability to understand and comply with IMP dosing instructions.

- If the participant is, in the investigator's opinion, no longer able or willing to comply with treatment instructions, then they should stop one or both IMP and revert to standard-care, even if they have not experienced an SAE or SAR.
- Participants who are assigned to patiromer and who have or develop hyperkalaemia (serum potassium >5.0mmol/L), even if they have been withdrawn from spironolactone or eplerenone IMP, may continue on or restart patiromer.
- For participants with recurrent (two or more within a 6 month period) or life-threatening hyperkalaemia, investigators should reduce the dose of spironolactone or eplerenone to a maximum of 25mg/day or less (this includes a zero-dose), unless in the opinion of the investigator the benefit/risk ratio of receiving higher doses of spironolactone / eplerenone IMPs is still believed to be positive (e.g. the participant's heart failure has responded well to higher doses of spironolactone or eplerenone). Participants assigned to patiromer should have the doses adjusted to achieve a serum potassium between 4.1 to 4.9mmol/L (inclusive).

IMP may be re-initiated at any time if the investigator believes it is safe to do so and the participant is willing. However, participants should continue to have their protocol-specified assessments as far as possible whether or not on therapy. Reasons for withdrawal will be recorded.

Participants who withdraw from IMP will not be replaced. This view may be revised by the IDMC.

The IDMC may recommend that the trial should be stopped for efficacy, safety or futility and will inform the TSC of this decision.

